#### 27.1.4. Pregnancy

Any woman who should become pregnant while on study will have the option of remaining on TDF/FTC and follow a separate complementary schedule of follow-up in clinical collaboration with high-risk obstetric (MFM) providers and. Details of this follow-up can be found in the MOPS. All such individuals will be reported to Gilead per FDA-mandated post-marketing requirements and registered by Gilead in the antiretroviral pregnancy registry to be followed until pregnancy outcome can be determined.

### 27.2. Social Harms

Although study sites will make every effort to protect participant privacy and confidentiality, it is possible that participants' involvement in the study could become known to others, and that social harms may result (i.e., because participants could be perceived as

being HIV-infected or at "high risk" for HIV infection). For example, participants could be treated unfairly, or could have problems being accepted by their families and/or communities. Social harms that are judged by the core investigators to be serious or unexpected will be reported to the IRB(s) at least annually, or according to their individual requirements. Social harms will be collected and reported on CRFs during regular visits. In the event that a participant reports social harm, every effort will be made by study staff to provide appropriate care and counseling to the participant, and/or referral to appropriate resources for the safety of the participant.

### **27.3. Management of Suspected Acute Seroconversion (Primary HIV Infection - PHI)**

Should an enrolled participant present with signs and symptoms consistent with PHI, this should trigger immediate HIV EIA and Viral Load (VL) or NAT testing; any positive result should prompt immediate resistance testing and referral to HIV specialty care. Participants who seroconvert within the protocol will undergo evaluation as in the schedule of events (see Section 19) and be provided assistance as needed to establish care. If the subject is currently taking TDF/FTC a third antiretroviral would be recommended as soon as possible. If there is a delay in obtaining care then TDF/FTC should be discontinued until an adequate antiretroviral regimen can be started. If the seroconverting individual is not taking TDF/FTC they will be advised not to take TDF/FTC until a complete regimen can be acquired.

**27.4. Seroconversion Schedule of Events**

Table 2: Schedule of events for seroconversion	Detection of Seroconversion	4-week visit
Visit Windows	±7 days	±7 days
CD4 panel	X	X
Viral load	X	X
Stored Plasma	X	X
Whole Blood	X	
Linkage Services Provision/Assessment	X	X
Behavioral Risk and Drug and Alcohol Assessments	X	X

If visit unobtainable, then phone call will be made to participant for follow-up on linkage to care.

Viral load will be run on blood plasma stored from seroconversion visit and all prior study visits, done sequentially from date of seroconversion visit until undetectable viral load in blood plasma.

If not already being done as part SOE assessments.

Assessments will be based on those in the main SOE, and details can be found in the MOPS.

**28. CRITERIA FOR DISCONTINUATION**

**28.1. Temporary Medication Interruption**

Attempts should be made to avoid temporary interruption.

Symptoms should be managed aggressively and proactively in an attempt to avoid discontinuation, provided there is no laboratory evidence of toxicity and any symptoms are Grade 1 or 2. In the event of symptomatic Grade 3 or any Grade 4 toxicity, TDF/FTC should be discontinued immediately, the only exception being a toxicity indisputably not attributable to TDF/FTC administration, with the permission of the protocol PI.

In the event of inadvertent discontinuation due to missed appointments, loss of medication, or other unforeseen circumstances, treatment should be resumed as rapidly as possible. Treatment should ONLY be reinstated in the absence of signs/symptoms of PHI (Table 1 above).

If the amount of time since last dosing of TDF/FTC exceeds 14 days when the participant wishes to reinitiate PrEP, a negative rapid HIV EIA and HIV VL should be documented PRIOR to PrEP reinitiation. If a serum creatinine has not been performed for study purposes within the past 30 days, serum creatinine too should be repeated (and Creatinine Clearance calculated and documented) prior to medication re-initiation.

**28.2. Permanent Medication Discontinuation**

Permanent medication discontinuation prior to 48 weeks of treatment should be limited to participants who withdraw consent, have laboratory evidence of acute or chronic HIV infection, are so advised by HIV-treatment experts, or have severe toxicity as noted above.

Such participants should continue to be followed per the protocol SOE (Cohort or seroconversion, as appropriate), even though they are no longer taking study medication.

Additionally, participants who have persistently low TFV-DP levels (<1050 fmol/punch), are referred for targeted iNSC (first instance) and PrEP-STEPS (if followed by a suboptimal (<1050 fmol/punch) TFV-DP level at subsequent visit(s)). Refusal/failure to participate in PrEP-STEP programming by attending  $\geq 1$  visit within 30 days of request by study staff may be considered for medication discontinuation in discussion with the Protocol Chairs.

### **28.3. Program Discontinuation**

Participants should be discontinued from the program under the following circumstances:

- Request by the participant to withdraw from the program
- Participant, in the judgment of program physicians, is unable to comply with provisions of the protocol in such a way as to be more likely to result in harm to the participant

\*Discontinued participants should return any unused study medication to the site for destruction, per program SOPs.

## **29. DATA COLLECTION, STORAGE, AND MONITORING**

### **29.1. Protocol**

This protocol will be available in hardcopy and PDF formats with the current version and date.

### **29.2. Secure Database**

The study will utilize existing CCTG informatics infrastructure provided by the UCSD Center for AIDS Research Bioinformatics and Information Technologies (BIT) Core. The BIT Core will provide study staff at CCTG and LAC-PATH sites access to OCCAMS, open source biomedical research data platform, to manage overall study flow, including the collection of data between and during participant visits including self-assessment questionnaires, iTAB text messages, specimen, laboratories, STI results, medication use, reported side effects, etc. All data will be stored in the secure and redundant BIT Core informatics infrastructure that uses a robust security modeling consisting of a multi-level hardware/software firewalled network, secure hardware and software encryption, data auditing and access tracking procedures and completely redundant services hosted from two physically separated server facilities. This infrastructure will also provide regulated access and reporting of study data to the biostatistics research team and relevant providers on a need-to-know basis. It is the responsibility of the CCTG Data Unit to assure the quality of computerized data for this study.

Case report forms (CRFs) will be provided for each participant. Instructions concerning the recording of study data on CRFs will be provided by the CCTG Data Unit. Participants must not be identified by name on any CRFs. Participants will be identified by the PID provided by the CCTG Data Unit upon registration and the linkage to the PID will be kept in paper copy only in a locked cabinet in a secure office at the study sites available only to the site investigators. Participant self-reported surveys that are performed electronically will be automatically stored in the electronic database secured by the CFAR BIT group for the CCTG.

### **29.3. Participant Confidentiality**

In an effort to maintain confidentiality but allow tracking of public health resources, all program entrants will have a unique patient identifier code based on their study site. A date of birth will be requested from participants to allow two methods of identification required for study sample identification. All obligatory laboratory specimens, evaluation forms, and other records will be identified by coded PID and participant date of birth (DOB). All records will be kept in a locked cabinet. All computer entry and networking programs will be performed with only PIDs. Clinical information will not be released without written permission from the participant, except as necessary for monitoring by protocol QA/QC, IRB, sponsor(s) or FDA. All participants will sign and receive a copy of HIPAA regulations prior to study commencement. The original will be placed in the study chart, and a copy will be given to the participant.

### **29.4. Data Collection and Monitoring**

Close cooperation between the Protocol Chairs, study site Investigator(s), and other study team members will be necessary in order to monitor participant safety and to respond to occurrences of toxicity in a timely manner. The team will have regularly scheduled conference calls during the period of study implementation, and additional ad hoc calls will be convened if required.

During the course of the study, enrollment rates, with a racial/ethnic breakdown, will be provided to California HIV Research Program (CHRP) on a monthly basis. Study conduct (in terms of assessment completion, successful sample collection, and data completeness) will be reviewed on a quarterly basis by the protocol team. Follow-up rates for each visit as well as the number of screened participants versus the number of participants enrolled, including a tabular list of reasons for screen-failure, will be reviewed on a monthly basis by the Protocol Chairs.

The study site Investigators are responsible for continuous close monitoring of all AEs that occur among study participants after informed consent is signed. Accrual and summary of all Grade  $\geq 2$  signs and symptoms and all Grade  $\geq 3$  laboratory abnormalities will be prepared by the study team and reviewed by the Protocol Chairs monthly. The study team will also prepare a quarterly report of all AEs (regardless of grade), including the number and percentage of adverse events, to be reviewed by the Protocol Chairs. Serious adverse events, Grades 3 and 4 will be tabulated separately and reviewed by the Protocol Chairs.

### **29.5. Clinical Site Monitoring and Record Availability**

A clinical study monitor will perform an on-site review of individual participant records, including: consent forms, CRFs, and laboratory specimen records. Monitoring will ensure protection of study participants, compliance with the protocol, and accuracy and completeness of records. The monitor will also inspect regulatory files to ensure requirements are being met. Pharmacy drug storage and dispensing records will be reviewed to ensure appropriate pharmaceutical product storage and management.

Monitoring visits will occur when 10 participants are enrolled at each site, and then at 3-6 month intervals during the remainder of study conduct.

## **30. STATISTICAL CONSIDERATIONS**

A formal Statistical Analysis Plan (SAP) will be drafted and finalized prior to database lock. The SAP will contain a more detailed and/or comprehensive presentation of statistical methods and is the final authority for all statistical analyses. The following section briefly describes the planned statistical analyses. In case the language in this section differs from the language in the SAP, the SAP takes precedence.

### **30.1. Sample Size Rationale**

The LAC-PATH group will enroll 85 women and the CCTG group will enroll 50 women for a total of 135 women who will start PrEP. The target goal of the multimodal triaged adherence intervention for women will be to achieve 90% of women with a DBS level  $> 1050$  fmol/punch at any given time. The proportion and 95% confidence interval will be calculated. If we assume 90% of women with a DBS level  $> 1050$  fmol/punch at any given time and 100 women enrolled in the study, then the 95% binomial distribution confidence interval around the estimate will be 6% (i.e.,  $90\% \pm 6\%$ ).

### 30.2. Statistical Analysis Plan

The overarching goal of this proposal is to study the implementation of PrEP combined with comprehensive HIV prevention services for women living in Southern California. The research aims are to: i) measure PrEP adherence by intracellular TFV-DP and FTC-TP, self-report via text messages and CASI-based adherence assessments; ii) explore the characteristics of women seeking PrEP and assess PrEP awareness and knowledge including barriers and facilitators to PrEP; and iii) determine acceptability and feasibility of a multi-modal adherence-based HIV-prevention program.

**Primary Objective:** To measure adherence to oral TDF/FTC at weeks 4, 12, 24, 36, and 48 using both biological (dried blood spots) and self-reported measures through daily text messaging (iTAB).

#### Hypothesis I

Drug levels will be high among those who persist with PrEP over time, as measured by tenofovir-diphosphate (TFV-DP) level > 1050 fmol/punch at weeks 4, 12, 24, 36 and 48.

#### Hypothesis II

Intracellular TFV-DP concentrations levels will correlate with self-reported adherence by daily texting through iTAB,

For the primary analysis, we will measure adherence using a drug level cutoff consistent with 6 or more doses per week, as measured by TFV-DP level > 1050 fmol/punch at weeks 4, 12, 24, 36 and 48. This will be in the as-treated group who are on-PrEP (censoring those on permanent or temporary discontinuation). A descriptive analysis of the proportion of women achieving adequate adherence by week of study will be conducted. Baseline versus 48 weeks proportion of adherence will be compared via Fisher's exact test.

**In order to examine drug adherence surrounding the implementation of intensified interventions specific to women receiving targeted iNSC and those receiving PrEP-STEPS we will compare the change in levels pre- and post-intervention.**

Additional sensitivity analyses will be performed using alternative cutoffs of adherence. Intracellular FTC-TP levels will be compared to TFV-DP for discrepancy of recent dosing that would be reflective of the short half-life of FTC (past day) versus the past week of dosing that is informed by the long half-life of TDF.

Subgroup analysis will compare adherence and other outcomes between risk categories of women (e.g. serodiscordant partnerships with and without conception intentions, partner of elevated HIV risk, sex worker, recent STI, injection drug use, PEP users).

Adherence will be measured by self-report using daily text messaging through iTAB. We will validate iTAB reported adherence in women using the TFV-DP levels for correlation with the proportion of positive responses in the 34 days prior to the drug level (i.e. two half lives of TDF) in week 12, 24, 36 or 48 using the Spearman correlation coefficient.

The average days of adherence per week during this time will be calculated as number of days reporting doses taken in past 35 days divided by 35 multiplied by 7 and rounded to the nearest whole number. For each number of days per week of adherence (i.e. 0, 1, 2,3, 4,

5,6 and 7) the TFV-DP will be reported from mean (95% confidence interval) and median (IQR).

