- Outcomes: The primary outcome is adherence defined as the mean of quantitative intracellular TFV-DP in dried blood spots (DBS) at 4, 12, 24, 36 and 48 weeks on study. The proportion of women achieving TFV-DP concentrations > 1050 fmol/punch, thought to be reflective of protective levels of PrEP, will be characterized. Self-reported adherence as indicated by responses to the iTAB texting system will be compared to TFV-DP levels.

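### Change in TFV-DP across visits is tested only on a yes/no cut at 1050 fmol/punch, although the assay is quantitative; a model of log TFV-DP should carry the comparison, with the proportion above 1050 kept as the descriptive result

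*Combined protocol and SAP*

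**What the plan says.** Section 4 (Outcomes) defines the primary outcome on the full scale, as the "mean of quantitative intracellular TFV-DP in dried blood spots (DBS) at 4, 12, 24, 36 and 48 weeks on study". The proportion above 1050 fmol/punch appears there as an additional description.

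Section 30.2 (under Hypothesis II) works on the cut: "For the primary analysis, we will measure adherence using a drug level cutoff consistent with 6 or more doses per week". Proportions are to be described by week among women on PrEP. For change over time, baseline and "48 weeks proportion of adherence will be compared via Fisher's exact test". On robustness it says: "Additional sensitivity analyses will be performed using alternative cutoffs of adherence". No model of quantitative TFV-DP over visits is described.

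The same section does use uncut TFV-DP elsewhere. Around targeted iNSC and PrEP-STEPS, "we will compare the change in levels pre- and post-intervention". Levels are correlated with iTAB responses by Spearman's coefficient, and mean and median TFV-DP are tabulated by reported dosing days per week. For risk groups it says only: "Subgroup analysis will compare adherence and other outcomes between risk categories of women". It gives no scale, cut-off or test for that comparison.

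**The concern.** Section 6 treats maintenance of high adherence in women as a critical question. The one named test of maintenance turns a quantitative measurement into yes/no at a point where 90% of women are expected to fall on the same side. A real decline could then easily give a non-significant result and be read as adherence having held up. The sensitivity analyses would not reveal the problem, since they are cuts too. Section 16.5.1 justifies 1050 as a level for classifying adherence and triggering extra support. That is a reason to report the proportion, but it does not by itself require that change be tested on it.

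**Working it through.** **The plan's own figure.** Section 30.1 gives 90% ± 6% with 100 women. The Wald half-width is 1.96 × √(0.9 × 0.1 / 100) = 0.0588, so it reproduces. Section 30.1 states no power for any comparison.

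**Inputs from the documents.** 100 women and 90% above 1050 (section 30.1); a 0.05 significance level, two-sided as stated for secondary outcomes (section 30.2); a 17-day TFV-DP half-life (section 10).

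**Assumptions.** A fall to 80%; within-woman correlation ρ of 0.3 to 0.7; the shape of the TFV-DP distribution; complete data at both visits.

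**Shift model (log TFV-DP normal, all women move together).** The standardised shift is d = z(0.90) − z(0.80) = 1.282 − 0.842 = 0.44, whatever the SD. The paired t-test has noncentrality d√n / √(2(1 − ρ)):
- ρ = 0.3: 0.44 × 10 / √1.4 = 3.72, power about Φ(3.72 − 1.98) = 96%.
- ρ = 0.5: 0.44 × 10 / √1.0 = 4.40, power about 99%.
- ρ = 0.7: 0.44 × 10 / √0.6 = 5.68, power about 100%.

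**Mixture model (less favourable).** Good users have median 1500 and log SD 0.25; low users have median 500 and log SD 0.7. The share above 1050 is Φ(ln(1500/1050)/0.25) = 92.3% for good users and Φ(ln(500/1050)/0.7) = 14.5% for low users. A fall from 90% to 80% therefore means that the share of low users rises from (92.3 − 90)/(92.3 − 14.5) = 3% to (92.3 − 80)/(92.3 − 14.5) = 16%.

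**Power over time, 100 women, 90% to 80%, ρ from 0.3 to 0.7** (the tests on the cut and the mixture by simulation; Monte Carlo error 1 to 2 points):

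| Analysis | Shift | Mixture |
|---|---|---|
| Fisher's exact, as planned | 42–45% | about 44% |
| Paired exact (McNemar) on the cut | 50–66% | 48–60% |
| Paired t on log TFV-DP | 96–100% | 69–88% |

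Fisher's test ignores the pairing within women, so part of its deficit is a separate defect. The fair comparison is with the paired exact test. At ρ = 0.3 and 0.7 the log analysis gains 96 − 50 = 46 and 100 − 66 = 34 points under the shift, and 69 − 48 = 21 and 88 − 60 = 28 points under the mixture. The gain survives both the pairing correction and the less favourable distribution.

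**Risk groups, 90% v 75%, same mixture.**
- Groups of 67 and 68: Fisher 58%, t-test on logs 73%.
- Groups of 70 and 30, smaller group less adherent: 41% v 40%.
- Groups of 105 and 30, smaller group less adherent: about 50% v about 40%.

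Here the gain shrinks, vanishes or reverses.

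**Reference visit.** Table 1 (section 20) schedules no dried blood spot at baseline, so the reference must be a follow-up visit. With first-order accumulation, the fraction of steady state at day t is 1 − 2^(−t/17). At week 4 it is 1 − 2^(−28/17) = 0.68. With unchanged dosing the week-48 to week-4 ratio would be about 1/0.68 = 1.47, which would look like improvement. At week 12 the fraction is 1 − 2^(−84/17) = 0.97, and the ratio is about 1.03.

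**The case against.** **The proportion above 1050 is the study's stated question.** Hypothesis I, the 90% target and the trigger for intensified support all use 1050, and section 16.5.1 gives a reason for it. The study is sized for interval width, not power. A geometric mean ratio can also move without any woman crossing 1050. All of this stands, and it is why the proportion should remain the descriptive primary result. It does not justify making the cut the only basis for testing change.

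**A reader might infer that every comparison of drug levels is dichotomised.** The documents do not support that. The comparison around intensified counselling is stated on levels, the iTAB validation uses uncut values, and mean levels are tabulated by reported dosing.

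**A reader might also infer that risk groups are compared on the cut, with a large loss of power.** The sentence names no scale or test, and section 4 would support a reading on the full scale. The loss there also depends on the distribution. Section 10 reports that 20% of participants in an earlier study had persistently undetectable drug. That makes a mixture plausible, and with a small, less adherent group the cut can do as well as logs or better.

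**The formal plan may already contain a model.** Section 30 calls itself brief and gives precedence to a formal SAP to be finalised before database lock. Such a document is not among those supplied, so this cannot be ruled out. It also means that the change can still be made within the plan's own process.

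**Conclusion.** The point holds for the comparison across study visits and for the adherence sensitivity analyses. As written, a fall from 90% to 80% above 1050 in 100 women would be missed more often than not (about 44% power). Correcting the pairing alone raises power only to about 48–66%. The same blood spots on the log scale give about 96–100% under a shift and 69–88% under the mixture. These figures rest on the assumed size of fall, correlation and distributions, and on 100 women with data at both visits. The primary analysis is limited to women on PrEP, so the number at week 48 may be smaller.

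For risk groups the supportable criticism is that the scale and test are unstated. A general power-loss figure cannot be claimed there, since the gain can disappear or reverse. The change is worth making because the present wording invites a non-significant test to be read as maintained adherence, and because it brings section 30.2 closer to the outcome defined in section 4.

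**What to change.** In section 30.2, or in the formal SAP before database lock:

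- Keep the weekly proportion above 1050 with its 95% confidence interval as the descriptive primary result.
- Replace the Fisher comparison with a linear mixed model of log TFV-DP, with visit as a factor and a random intercept per woman. Report the week-48 to week-12 geometric mean ratio with its 95% confidence interval, and show the proportions above 1050 beside it.
- Do not use week 4 as the reference visit. It stays in the descriptive table.
- State one fixed rule for values below quantification and vary it once as a check.
- For risk categories, state the scale and test. Report the same model with risk category added as supportive, beside the proportions above 1050.

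The cost is SAP wording and a standard model on data already collected. There are three downsides. A geometric mean ratio is less directly tied to the 1050 level, week 4 drops out of the comparison, and unquantifiable values need a stated convention.

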#### 4. STUDY SCHEMA

- Design: AEGIS is an open-label single-arm longitudinal clinical trial to estimate medication adherence and retention in a PrEP HIV prevention program that implements a combination intervention strategy that uses text-messages (iTAB) and a staged adherence counseling support strategy titrated from real-time drug levels in women at-risk for HIV acquisition.
- Duration: Each participant will be on PrEP with medication adherence support for 48 weeks after enrollment with a post study follow-up at 60 weeks. The primary endpoint will be measured at 48 weeks.
- Sample Size: A total of 135 participants will be enrolled (50 at CCTG sites and 85 at the LAC-PATH site).
- Study Population: Eligible participants will include HIV-uninfected cis-gender women at least 18 years of age and who are at risk for HIV acquisition.
- Intervention: All participants will be given PrEP with tenofovir disoproxil fumarate (TDF) + emtricitabine (FTC) fixed dose combination prescribed to be taken once daily. All participants will receive the combined intervention of iTAB text messaging adherence reminders and intensive Next Step Counseling (iNSC). The iTAB system consists of daily, personalized, automated 2-way text messages to maintain adherence and retention, and iNSC is a brief, strengths-based discussion initiated at each clinic visit, typically with delivery of negative HIV-test results, focused on promotion of sexual health protection through behavioral and biomedical (adherence) strategies. Participants that have a low intracellular tenofovir diphosphate (TFV-DP) concentration will receive escalated, targeted adherence support (see study schema). All participants will receive access to PrEP in accordance with standardized comprehensive methods of prescribing and clinical assessments that include safety monitoring as well as regular HIV and sexually transmitted infection (STI) screening.
- Regimen: TDF 300 mg + FTC 200 mg fixed dose combination will be given orally once daily starting at the baseline visit (month 0) and continued throughout the study.

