The Partners-PrEP study (a population of heterosexual serodiscordant men and women in Kenya and Uganda) also found that drug levels strongly predicted TDF/FTC and TDF efficacy - detectable drug (using a more sensitive assay than the primary iPrEx data) predicted 86% efficacy for TDF alone, and 90% efficacy for TDF/FTC (contrast 67% and 75%, in the overall population, respectively). The Partners-PrEP study found three distinct patterns of adherence: 1. Seventy percent of participants had sustained TFV drug levels >40 ng/mL; 2. Ten percent of the population had levels that were detectable most of the time (10-40 ng/mL), but dipped occasionally to undetectable levels; and 3) Twenty percent of the population had persistently undetectable drug levels (52). It is probable that prospective, real-time identification of these non-adherent populations (although it remains unclear what percentage this would represent in iPrEx [the MSM population studied to date] – one would suspect the overwhelming majority) and applying intensive adherence interventions would be critical to the success of a PrEP effort.

In this study we will use intracellular TFV-DP from DBS as our primary outcome measure of adherence. Anderson and Castillo-Mancilla have developed technology using LC-MS/MS to measure intra-erythrocytic TFV-DP levels, which provide a measure of average tenofovir exposure (adherence) over the preceding 30-90 days, not unlike a Hemoglobin A1C measurement (53). Such measurements can be made from DBS samples, which are stable over time and easy to handle. The key characteristic that enables TFV-DP to be used as an adherence biomarker is the 17-day half-life of TFV-DP in red blood cells. A similar long-term objective measure of adherence, tightly correlated with virologic suppression has been validated using scalp hair samples (54). However, sampling of scalp hair has proven variably acceptable among diverse populations (unpublished data, ACTG A5257).

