### **16.5.1. Real-time intraerythrocytic drug levels**

Blood will be collected for intraerythrocytic TFV-DP drug level assays at each follow-up visit. Prior pharmacokinetic/pharmacodynamics studies have established levels for categorization of dosing for interpretation of DBS levels. Given the high adherence requirement for women to achieve protective levels, a threshold of 1050 fmol/punch corresponding to 6 or more doses per week will be used as the threshold for optimal adherence (28, 60). Levels below this threshold will be considered to represent suboptimal adherence and will trigger intensification of adherence support as outlined below.

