iTAB has found to be associated with high adherence and valid as a measure of self-reported adherence in CCTG 595, an open-label, two-arm, controlled, randomized 1:1 clinical trial of iTAB versus standard of care (no iTAB) as a demonstration project evaluating retention and adherence to PrEP in 400 MSM and transgender women over 48 weeks. In a preliminary analysis of intracellular TFV-DP levels in Week 12 DBS among the first 152 participants in the iTAB arm (71), we found that adherence in the iTAB arm was high with a

mean TFV-DP of 1352 fmol/punch, which equates to taking 6 of 7 doses of PrEP a week. Since CCTG 595 is an ongoing study, the comparison of iTAB to a control arm that did not receive iTAB text has not been performed yet. The preliminary data also show a significant correlation between TFV-DP concentrations and proportion of positive (“Yes, I took my meds.”) iTAB responses ( $r=0.26$ ,  $p=0.01$ ) supporting iTAB as a valid measure of adherence. These findings support the use of iTAB as a valid self-reported measure for adherence that can discriminate between adequate and inadequate PrEP adherence.

In this study, all participants will receive text messaging through the iTAB system. At the baseline visit, the study coordinator will introduce the participant to the iTAB texting system and provide training on iTAB framework for texting supportive reminder messages and tracking adherence. If a participant does not have unlimited text messaging, the study will provide participant reimbursement to pay for unlimited text messages. In cases where a participant does not have a phone, an appropriate cell phone with an unlimited texting plan will be provided.

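### At week 4 the 1050 fmol/punch cut cannot carry the same doses-per-week meaning as at later visits, and drug accumulation can pass for a targeted-iNSC effect in women triggered at week 4

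*Combined protocol and SAP*

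**What the plan says.** Section 4 has TDF/FTC "given orally once daily starting at the baseline visit (month 0"), and section 10 rests the use of TFV-DP as an adherence marker on "the 17-day half-life of TFV-DP in red blood cells". Section 16.5.1 sets the cut: "a threshold of 1050 fmol/punch corresponding to 6 or more doses per week will be used as the threshold for optimal adherence". The primary analysis in section 30.2, among women on PrEP, uses a "drug level cutoff consistent with 6 or more doses per week, as measured by TFV-DP level > 1050 fmol/punch at weeks 4", and likewise at weeks 12, 24, 36 and 48. It adds: "A descriptive analysis of the proportion of women achieving adequate adherence by week of study will be conducted".

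A level below 1050 triggers targeted iNSC, typically about 10 days after the visit, and a repeat low level leads to PrEP-STEPS (section 16.5.3). For women who receive either, section 30.2 says only that "we will compare the change in levels pre- and post-intervention".

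The iTAB correlation in the same section looks back 34 days and leaves out week 4: "i.e. two half lives of TDF) in week 12, 24, 36 or 48 using the Spearman correlation coefficient". The one dated level-to-dose figure is in section 16.5.2, from week 12 of another study in MSM and transgender women: "mean TFV-DP of 1352 fmol/punch, which equates to taking 6 of 7 doses of PrEP a week".

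**The concern.** A marker with a 17-day half-life is still accumulating after 28 days of dosing. Section 10 itself describes it as averaging exposure over 30 to 90 days, which is longer than the time on drug at week 4. One cut cannot stand for one dose rate both during accumulation and at plateau.

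Two results are at stake. The week-4 proportion with adequate adherence would be too low as a statement about doses taken, so a by-week trend that starts there would show an improvement that is partly accumulation. In addition, women counselled after a low week-4 level would show a higher week-12 level even if they changed nothing. With no control arm, that rise could be credited to targeted iNSC.

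**Working it through.** **The plan's own figures.** 1.96 × √(0.9 × 0.1 / 100) = 5.9%, which agrees with the stated ±6%. The 34-day look-back is 2 × 17 days. It does not fit into the 28 days before week 4, although the plan gives no reason for leaving that visit out. The documents state no accumulation fraction to reproduce.

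**Model.** Assume constant dosing from day 0, a zero starting level (no baseline DBS is scheduled) and first-order kinetics. The fraction of steady state at day d is f(d) = 1 − 2^(−d/17).

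| Day | 14 | 28 | 42 | 70 | 84 | 98 | 168 |
|---|---|---|---|---|---|---|---|
| f(d) | 0.435 | 0.681 | 0.820 | 0.942 | 0.967 | 0.982 | 0.999 |

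**Dose meaning of 1050 at week 4.** Assume levels proportional to dose, with S the steady-state level at 6 doses/week. The expected level of a woman taking 6 of 7 doses is S × f(d). The doses per week for an expected 1050 are 6 × 1050 / (S × f(d)).

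- *Section 16.5.2 figure.* S = 1352 if that value is a plateau, or 1352 / 0.967 = 1397 if it is a week-12 level. At day 28 the expected level is 920 or 951, and 6.8 or 6.6 doses/week are needed. At day 84 the need is 4.8 or 4.7. A woman taking every dose is expected at 1074 or 1110 at day 28.
- *If 1050 were the mean plateau level at exactly 6 doses/week* (an assumption). At day 28 the expected level is 1050 × 0.681 = 715.

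On either basis, the dose rate needed at day 28 is 0.967 / 0.681 = 1.42 times that needed at day 84.

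**Pre/post change at constant dosing.** Assume pre is the triggering DBS and post is the next scheduled DBS.

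- Week 4 to 12: f(84)/f(28) = 1.421, or +42%. If the ±14-day window in section 20 applies to both visits, the range runs from f(70)/f(42) = 1.150 to f(98)/f(14) = 2.257, or +15% to +126%.
- Week 12 to 24: f(168)/f(84) = 1.033, or +3% (+2% to +6% across windows).
- Later intervals: 0.1% at nominal days, and at most about 0.2% across windows.

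Half-lives of 14 and 20 days, taken only as a sensitivity range, give +31% and +52% for week 4 to 12.

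**Proportions.** A 3% shift in level is not a 3% shift in the proportion above a cut. With a lognormal spread and an assumed between-woman CV of 20–30%, the share of 6-of-7 dosers above 1050 rises by about 3 to 6 points from week 12 to week 24. This is an illustration, because the documents give no CV.

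**The case against.** The strongest reply is that the cut may be meant as a concentration. Section 4 calls levels above 1050 protective, and on that reading a low week-4 level is simply low. That stands, and the proportion above 1050 at week 4 remains a valid description of concentration. It does not rescue the doses-per-week reading in sections 16.5.1 and 30.2.

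A second reply is that the analyses are modest. The by-week proportion is labelled descriptive, the pre/post comparison names no test, and a later SAP takes precedence (section 30) and may define the samples. This limits the weight of the point, but nothing in the text supplied handles time on drug. The alternative cutoffs are not tied to visit, and neither the FTC-TP comparison nor the restriction to women on PrEP adjusts for accumulation.

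Third, a reader might infer that even perfect daily dosing fails the cut at week 4. That requires 1050 to be the mean plateau level at exactly 6 doses/week (then 1050 × 7/6 × 0.681 = 834). Section 16.5.1 gives only a threshold for 6 or more doses, and on the section 16.5.2 figure a daily doser is expected above 1050. Nor do the two figures necessarily conflict, since one is a classification threshold and the other a group mean in a different population.

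It would also be too strong to say that every 6-of-7 doser falls below 1050 at the week-4 visit. If the ±14-day window applies, on the section 16.5.2 figure she is expected at 1108 to 1145 by day 42.

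**Conclusion.** The concern holds in a limited form. At nominal week 4 the level is about 68% of steady state, so reading 1050 as 6 or more doses per week understates dose-based adherence at that visit. The direction follows from the protocol's half-life and start of dosing. The size depends on a calibration that the documents do not settle: about 920–951 for a 6-of-7 doser on the section 16.5.2 figure, and about 715 if 1050 is taken as the plateau mean at exactly 6 doses/week.

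For women triggered at week 4, accumulation alone adds about 42% by week 12. This assumes constant uninterrupted dosing, nominal days, and the two sample definitions above.

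A reader might infer that the primary result or all pre/post comparisons are compromised. The documents do not support that. The week-48 endpoint, the ±6% precision and the concentration reading of 1050 are unaffected. First triggers at week 12 carry a level change of about 3% at nominal days, and later ones almost none. PrEP-STEPS needs a repeat low level, so on scheduled visits it falls in the same range. Counts of women triggered or crossing the cut would rest on an assumed CV and assumed dosing, and are not findings.

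**What to change.** 1. In section 30.2, or in the SAP, apply the doses-per-week reading of 1050 from week 12 onward. At week 4, report the quantitative level and the proportion above 1050 as a concentration only, not as an adherence rate or the start of an adherence trend. Section 5.1 states levels without doses per week and needs no change to dose wording.

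2. For targeted iNSC, define pre as the triggering DBS and post as the next scheduled DBS. Exclude week-4 pre values from the main comparison, or report those women separately. As a sensitivity analysis, include them with each level divided by 1 − 2^(−d/17), where d is days since first dose, limited to women without a dosing interruption. State that regression to the mean remains, because women are selected on a low level.

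3. Before using any accumulation-scaled cut, clarify how the 1050 threshold (section 16.5.1) relates to the 1352 mean (section 16.5.2).

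The use of 1050 at week 4 as a trigger for support (sections 16.5.1, 16.5.3 and 28.2) must be reconciled with the half-life in section 10 by the protocol team. No clinical rule is proposed here.

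The cost is wording and re-analysis of samples already planned. There is one fewer visit in the dose-based classification, and fewer women in the main pre/post comparison. Those lost could be most of the first triggers, which is why separate reporting is offered as the alternative. The scaled sensitivity analysis relies on the 17-day half-life, a zero starting level and uninterrupted dosing.
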